Radiologic tumor assessment will be performed at baseline, cycle 3 day 1, cycle 5 day 1 and at the end of every 3 cycles beyond cycle 5 (one cycle = 21 days). All patients including those removed from the study due to unacceptable toxicity, will undergo radiologic tumor assessment within 30 days of the time of discontinuation (End of treatment). If a scan is performed within 30 days of end of treatment is available, the previous scan will be accepted. Patients who show disease progression at the first instance could continue to receive the treatment for up to 2 more cycles depending upon the percentage of increase in the tumor. Patients up to 30% increase in tumor burden would be allowed to continue the treatment until the second confirmatory scan if the patient is deriving clinical benefit in the treating Physician's opinion. Patients who continue treatment beyond progression would undergo another confirmatory scan at the end of 2 more cycles and if the progression is confirmed they will be come off the study.

4 Eligibility Criteria

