5.2.2 Anti-emetic Therapy

There are no restrictions on the use of antiemetic therapy for this trial. Medications to prevent emerging toxicities are permitted as long at their use does not conflict with other guidelines in this protocol.

5.2.3 5.2.3 Other Anticancer or Experimental Drugs

Treatment with other anticancer or experimental drugs is not permitted for patients treated on this protocol.

5.2.4 5.2.4 Palliative and supportive care

All palliative and supportive care necessary for optimal care of the patient, excluding radiation therapy should be provided while on study. Patients requiring radiation therapy for palliation will be removed from the study. Treatment with growth factors is excluded except to treat febrile neutropenia.

5.3 **Duration of Therapy**

In the absence of treatment delays due to adverse events, treatment may continue until one of the following criteria applies:

Confirmed radiographic disease progression. In the absence of clinical progression and occurrence of radiographic progression, patients will have the option to remain on study.

Intercurrent illness that prevents further administration of treatment

Unacceptable adverse events

Patient required > 2 dose reductions

Patient becomes pregnant

Patient decides to withdraw from the study

General or specific changes in the patient's condition that render the patient unacceptable for further treatment in the judgment of the investigator.

5.4 **Duration of Follow up**

All subjects will be followed post-treatment until death, withdrawal of permission to record at least survival data, or subject is lost to follow-up every 30 days (\pm 7 days) after coming off study. When available, tumor imaging will be collected for all patients who accrued to the study and receive at least one dose of ONC201. All subjects will be contacted every 30 days to assess for study-treatment related toxicities, initiation of any new anti-cancer treatments, and survival status. Contact may be performed by a site visit, telephone contact, e-mail, or mail. The date of death, initiation of any new anti-cancer treatments and date of last contact should be documented if this information is available.

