For Arm C: Blood draws taken at baseline (pre-dose), 2 hours ± 15 minutes, 24 ± 1 hours (pre-day 2 dose), 26 ± 2 hours, 48 hours ± 3 hours, 72 hours ± 12 hours, and Day 8 and 15 ± 24 hours following the first administration of ONC201. Blood will also be collected predose for Cycle 2, Cycle 3 and every odd cycle beyond Cycle 3.

Refer to lab manual for collection window of samples. Blood will also be collected at the end of treatment visit for correlative studies. Immune cytokines and effectors will be assessed on serum samples obtained for pharmacodynamic analyses.

Refer to lab manual for Biospecimens processing and handling requirements.

8.3 **Blood for immune cell studies**

Peripheral blood mononuclear cells (PBMCs) will be harvested and investigated for effects of ONC201 on the immune system. One EDTA tube of blood will be collected at the same time points as the red-top tubes are collected: Baseline and 2 hours, 24 hours, 48 hours, and 72 hours after the first dose of ONC201; Cycle 1 Day 8; Cycle 1 Day 15; pre-dose for the first day of cycle 2, cycle 3 and every odd cycle beyond cycle 3. Blood will also be collected at the end of treatment visit for correlative studies. Collection of PBMCs is not required for Arm C.

8.4 **Blood for pharmacokinetics**

The plasma obtained prior to the isolation of PBMCs (see Section 8.3) will be used to determine concentration of ONC201. No additional blood samples will be collected from the patient for these studies. For Arm C, plasma for pharmacokinetics will be collected at baseline (pre-dose), 2 hours \pm 15 minutes, 24 \pm 1 hours (pre-day 2 dose), 26 \pm 2 hours, 48 hours \pm 3 hours, 72 hours \pm 12 hours, and Day 8 and 15 \pm 24 hours following the first administration of ONC201. Blood will also be collected pre-dose for Cycle 2, Cycle 3 and every odd cycle beyond Cycle 3.

9 Study Calendar

Study visits and procedures may be scheduled with a +/-2 business day window except for Screening procedures (-14 days) and neuroimaging (MRI/CT) Screening, Cycle3 and every odd cycle day 1 (+/-7 days). One treatment Cycle is defined as 3 weeks (21 days).

Study Activity	Screening	C1D1	C1D2	C1D3	C1D8	C1D9	C1D10	C1D15	C1D16	C2D1	C2D2	Cycle 3, and every odd cycle, day 1 ⁸	Off- treatment	Follow-up 30 days (+/- 3 days) ⁵	Survival Follow Up (30 +/- 7 days)
Informed Consent	Х														
Medical History	Х														
Inclusion/exclusion criteria	х														
Concurrent meds ¹	х	Х								Х		Х	Х		

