11.1 Response Evaluation Criteria in Solid Tumors (RECIST)

The Response Evaluation Criteria in Solid Tumors (RECIST v 1.1) criteria will be used for objective tumor response assessment. Response assessment would be performed at C3D1, C5D1 and at the end of every 3 cycles beyond cycle 5. All patients, including those removed from the study due to unacceptable toxicity, would undergo radiologic tumor assessment at the time of discontinuation (End of treatment). Patients who show disease progression at the first instance could continue to receive the treatment for up to 2 more cycles if the increase in tumor burden is up to 30%. Patients who continue treatment beyond

progression would undergo another confirmatory scan at the end of 2 more cycles, and if the progression is confirmed, they will be come off the study.

11.2 **Definitions**

Evaluable for adverse events. All patients will be evaluable for adverse events from the time of their first treatment with ONC201.

Evaluable for progression-free survival. All Arm B patients who have received at one dose of ONC201 will be considered evaluable for progress-free survival as the primary endpoint.

Evaluable for objective response. Only those patients who have measurable disease present at baseline, have received at least one cycle of therapy, and have had their disease reevaluated will be considered evaluable for response. These patients will have their response classified according to the definitions stated below. (Note: Patients who exhibit objective disease progression prior to the end of cycle 1 will also be considered evaluable.)

Evaluable Non-Target Disease Response. Patients who have lesions present at baseline that are evaluable but do not meet the definitions of measurable disease, have received at least one cycle of therapy, and have had their disease re-evaluated will be considered evaluable for non-target disease. The response assessment is based on the presence, absence, or unequivocal progression of the lesions.

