The duration of overall CR is measured from the time measurement criteria are first met for CR until the first date that progressive disease is objectively documented.

Duration of stable disease: Stable disease is measured from the start of the treatment until the criteria for progression are met, taking as reference the smallest measurements recorded since the treatment started, including the baseline measurements.

11.7 **Progression-Free Survival**

Progression-free survival (PFS) is defined as the duration of time from start of treatment to time of progression or death, whichever occurs first. Progression-free survival (PFS) is defined as the time from registration to objective disease progression or death, whichever occurs first. PFS2 will be defined as the percentage of patients who exhibit PFS for >8 weeks (>56 days). Patients who have not progressed or died and are lost to follow up at 2 months will be replaced.

12 Statistical Considerations

12.1 **Primary Endpoint and Interim analyses**

Arm A and C will assess intratumoral drug concentrations and pharmacodynamics. Arm B will assess progression-free survival rate at two month following treatment initiation as primary endpoint. Patients with biopsiable disease may represent a biased subset of the overall target population since some sites of metastases will not be amenable to biopsy and therefore comparing these patients' outcomes to historical controls may not be appropriate. For this reason, only patients in Arm B will be evaluated for the primary endpoint of PFS2.

No interim analyses will be performed for Arm A or C. Pharmacodynamic effects will be evaluated by assessment of tissue biomarkers based on mechanism of action and preclinical tumor cell sensitivity studies. IHC analyses for biomarkers such as ATF4, CHOP, and DR5 will be summarized using descriptive statistics.

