Arm B uses a Simon two-stage mini-max design [27] to evaluate the hypothesis that ONC201 will extend progression-free survival at 2 months beyond historical controls for this disease, as performed for buparlisib (NCT01397877). Historical controls for type II endometrial cancer show the null hypothesis to be 40% progression free survival at 2 months. To show the alternative hypothesis that >70% of patients exhibiting progression-free survival at 2 months with 90% power and an alpha= 5%, 24 evaluable patients are required for this arm. The probability for early termination under the null hypothesis is 63.3%.

An interim futility analysis will be performed for Arm B when the 10 evaluable patients in Arm B are evaluable for PFS2, as defined in section 11.7. In stage 1 of the study, if at least 5 of the first 10 evaluable patients exhibit progress-free survival for at least two months from treatment initiation (as defined in section 11.7), recruitment will be continued until a total of 24 evaluable patients have been enrolled for this arm. In stage two, if at least 14 patients demonstrated progress-free survival at 2 months ONC201 will be considered to have shown sufficient efficacy to warrant further study.

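### Sections 11.2 and 11.7 give different sets of Arm B patients for the primary endpoint, and nothing says which set the 5-of-10 and 14-of-24 rules use

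*Combined protocol and SAP*

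**What the plan says.** **Primary-endpoint set.** Section 11.2 states: "All Arm B patients who have received at one dose of ONC201 will be considered evaluable for progress-free survival as the primary endpoint". It makes no exception for loss to follow-up.

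**Replacement.** Section 11.7 defines PFS2 as the percentage of patients with PFS beyond 56 days and adds: "Patients who have not progressed or died and are lost to follow up at 2 months will be replaced".

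**Decision rules.** Section 12.1 sets the futility look "when the 10 evaluable patients in Arm B are evaluable for PFS2, as defined in section 11.7". Arm B continues "if at least 5 of the first 10 evaluable patients exhibit progress-free survival for at least two months from treatment initiation". The arm is positive if at least 14 of 24 evaluable patients succeed. The stated design is a null of 40%, an alternative of 70%, alpha 5%, power 90% and early termination of 63.3% under the null.

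**Assessment and follow-up.** Section 3: "Radiologic tumor assessment will be performed at baseline, cycle 3 day 1, cycle 5 day 1". The Section 9 calendar gives these scans a window of 7 days either way. Section 3 also requires a scan around discontinuation, with a waiver: "If a scan is performed within 30 days of end of treatment is available, the previous scan will be accepted". After treatment, Section 5.4 says: "All subjects will be contacted every 30 days to assess for study-treatment related toxicities, initiation of any new anti-cancer treatments, and survival status". It also collects tumor imaging when available.

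**Meaning of lost.** Section 12.2 describes lost to follow-up as withdrawal before evidence of progression or death and censors such patients, but only for the Kaplan-Meier analysis of PFS.

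**Response.** Section 11.2 asks for measurable disease, one cycle and re-evaluation, and keeps patients who progress before the end of cycle 1. Section 12.3.2 asks for two cycles and re-evaluation, and then lists early-death categories.

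**The concern.** A dosed patient who is event-free and then lost by 2 months is evaluable under 11.2 and replaced under 11.7. Section 12.1 counts evaluable patients, so she is either inside or outside the 10 and the 24 depending on which section is followed. If she is inside, nothing says whether she is a success or a failure.

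A second group is unclear. A patient who stops early, has no post-baseline scan and stays in 30-day contact may or may not be lost in the sense of 11.7. The contacts listed in 5.4 do not record progression, and after an early stop the scan accepted under the Section 3 waiver can be the baseline scan.

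The trial is open-label and single-arm, and it is judged against a fixed historical 40%. If the denominator is settled only when a patient has been lost, it can be settled with the outcomes in view.

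A secondary matter has the same cause. Sections 11.2 and 12.3.2 cannot both define the response denominator, and the two-cycle version leaves out early failures.

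**Working it through.** **1. Reproduce the design.** Inputs from Section 12.1: p0 = 0.40, p1 = 0.70, continue if X1 ≥ 5 of 10, positive if the total is ≥ 14 of 24.

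- P(early termination) = P(X1 ≤ 4 | n = 10, p)
- P(positive) = Σ over x = 5..10 of P(X1 = x | 10, p) × P(X2 ≥ 14 − x | 14, p)

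At p = 0.40, early termination is 0.6331 (stated 63.3%) and P(positive) is 0.0482. At p = 0.70, P(positive) is 0.9009 (stated 90%). The cut-offs are correct when 10 and 24 patients have known 2-month status.

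**2. One lost patient at stage 1.** Take 4 successes, 5 failures and 1 lost.

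- Kept as a non-success: 4/10 < 5/10, so Arm B stops.
- Replaced: Arm B continues if the replacement succeeds, with probability 0.40 (null) to 0.70 (alternative), taking those rates as unaffected by loss.

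**3. How often a loss occurs.** The documents give no loss rate L, so 5% and 10% are assumed. P(at least one loss in n) = 1 − (1 − L)^n.

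| L | first 10 | 24 |
|---|---|---|
| 5% | 40% | 71% |
| 10% | 65% | 92% |

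**4. False-positive rate under replacement.** Let f be the share of lost patients who would have failed (also not in the documents). Under the null the success rate among retained patients is p = (0.40 − L(1 − f))/(1 − L). For example, L = 0.10 and f = 1 gives 0.40/0.90 = 0.444; f = 0.30 gives 0.33/0.90 = 0.367. Putting p into the formula in step 1:

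| f | L = 5% | L = 10% |
|---|---|---|
| 30% | 3.4% | 2.3% |
| 50% | 4.3% | 3.8% |
| 60% | 4.8% | 4.8% |
| 75% | 5.7% | 6.7% |
| 100% | 7.3% | 11.1% |

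At f = 60% loss is unrelated to outcome under the null, and the rate is unchanged. Above 60% it rises; below, it falls.

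**5. First 10 and 24 dosed, lost scored as non-success.** The success rate is p − L(1 − f). With unrelated loss, f = 0.60 under the null and 0.30 under the alternative.

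| L | null p | P(positive) | alternative p | P(positive) |
|---|---|---|---|---|
| 5% | 0.380 | 3.1% | 0.665 | 82.4% |
| 10% | 0.360 | 1.9% | 0.630 | 72.0% |

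Every non-lost patient among the first 10 (or 24) dosed is also among the first 10 (or 24) evaluable under replacement. A positive result here therefore implies a positive result under replacement. The two rules then disagree with probability equal to the difference. Under the alternative this is 90.1 − 82.4 = 7.7% at L = 5% and 90.1 − 72.0 = 18.1% at L = 10%. Under the null it is 4.8 − 3.1 = 1.7% and 4.8 − 1.9 = 2.9%.

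**6. What scan timing says about f.** C3D1 is day 2 × 21 + 1 = 43 and C5D1 is day 4 × 21 + 1 = 85. With 7 days either way, no scheduled scan falls on days 51 to 77. A patient lost after a clean C3D1 scan has little opportunity for a documented failure by day 56. A high f is plausible mainly for losses before C3D1. The documents do not say how losses divide.

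**7. Response rate (illustration, counts assumed).** With 3 responders among 24 dosed and 6 excluded for not reaching two cycles and a re-scan, the rate is 3/18 = 16.7%, against 3/24 = 12.5%.

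**The case against.** The strongest reply is that there is one workable rule. Section 11.2 is general, 11.7 is the specific exception, and 12.1 refers to 11.7 twice when it states the decision rules. Section 3 also plans for 10 to 24 evaluable patients, which fits replacement. If loss is unrelated to outcome, this rule leaves alpha and power unchanged. Most of this stands: replacement is probably what was meant. But 11.7 does not define evaluable, the only explicit definition for this endpoint is in 11.2, and no precedence is stated.

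A reader might infer that patients who stop early have no rule at all. That goes too far. The Section 12.2 description of lost to follow-up could be taken to cover them, Section 3 calls for a scan around discontinuation, 5.4 collects available imaging, and 11.5.3 asks for effort to document progression after treatment stops. These passages limit the number affected. They do not settle the rule, because 12.2 speaks only of the Kaplan-Meier analysis and withdrawal need not mean stopping treatment.

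A reader might also infer that success should require an on-treatment scan. The documents do not support that. PFS in 11.7 does not depend on being on treatment, and such a condition would change the primary endpoint and cost power.

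On response, 12.3.2 already treats categories 4 to 9 as treatment failure. That stands, but it helps only for patients who enter the denominator.

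**Conclusion.** The inconsistency is in the current text and affects the go/no-go rule for Arm B. It should be fixed. It concerns only dosed patients who are event-free and lost, or never re-scanned, by 2 months; documented progressions and deaths count either way. The cut-offs themselves are not miscalculated.

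A reader might infer that replacement inflates the type I error. The documents do not support that as a general statement. It holds only if more than 60% of lost patients would have failed, and the rate falls if the share is lower. Neither the loss rate nor that share is given, so the percentages under loss are conditional on assumed values. The stage 1 example needs no assumed loss rate: one lost patient can separate stopping from a 40% to 70% chance of continuing.

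The mismatch in response denominators is also real, but it is secondary and does not touch the two cut-offs.

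**What to change.** 1. Reconcile 11.2, 11.7 and 12.1 so that one stated denominator drives both stages. If replacement stays primary, a sentence in 11.2 saying so is enough.
2. At both stages also report a sensitivity analysis on the first 10 and first 24 dosed Arm B patients, with lost or never re-scanned patients scored as non-successes against the same cut-offs of 5 and 14. Give the number, timing and reasons of losses.
3. State whether a patient off treatment, in contact, and without any post-baseline disease assessment is replaced or scored as a non-success. Any adequate post-baseline scan, on or off treatment, should count. Do not add an on-treatment scan requirement to the primary endpoint.
4. Use one response denominator in 11.2 and 12.3.2: all dosed patients with measurable disease at baseline, with anything other than CR or PR counted as non-response.

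**Cost.** Text changes and a little extra analysis, with no new visits or data. The primary decision loses no power if replacement stays primary. The sensitivity result is stricter: for a truly active drug it is positive with probability 82.4% or 72.0% at an assumed 5% or 10% unrelated loss, against 90.1%. If the sponsor made it the primary rule, those would be the power figures to restate. The reported response rate may be slightly lower.

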12.2 Analysis of Secondary/Exploratory Endpoints

All patients enrolled in the study who received at least 1 dose of ONC201 will be evaluated in the safety analysis using descriptive statistics including pre-treatment characteristics and concomitant treatment.

Adverse events and clinical labs will be graded according to NCI CTCAE Version 4.03. For labs without CTC grade definitions, results will be summarized as normal, abnormal or not done. Summary tables will present frequencies of patients experiencing at least one AE categorized by System Organ Class and Preferred Term according to MedDRA terminology. Listings will be prepared for each laboratory measure, and will be structured to permit review of the data by patient as they progress on treatment. Graphic displays and shift tables may be provided, as appropriate, to illustrate the results over time on study. ONC201 dose delays, dose modifications, drug exposure and duration of treatment will be also summarized.

Duration of response and duration of stable disease will be characterized using Kaplan-Meir estimates in the relevant subgroups.

Progression Free Survival (PFS) will be characterized using Kaplan-Meier curves. Median PFS will be calculated along with 95% confidence intervals. Patients who are lost to follow-up (who withdraw from the study prior to evidence of progression or death) will be censored.

12.3 **Reporting and Exclusions**

12.3.1 Evaluation of toxicity:

All patients will be evaluable for toxicity from the time of their first treatment with ONC201. Safety will be assessed by quantifying the toxicities and grades experienced by subjects who have received ONC201, including serious adverse events (SAEs). Other safety endpoints include laboratory safety assessments, vital signs and physical examinations.

A Bayesian method [27] will be used for toxicity monitoring based on the dose-limiting toxicity (DLT) rate. Patients in Arm A and Arm B will be monitored jointly for toxicity. Toxicities will be defined according to the Common Terminology Criteria for Adverse Events (CTCAE) version 4.03. DLT is defined as a clinically significant adverse event or abnormal laboratory value assessed as unrelated to disease progression, intercurrent illness, or concomitant medications and occurring during the first cycle on study that meets any of the following criteria:

- CTCAE grade 3 AST (SGOT) or ALT (SGPT) for > 7 days
- CTCAE grade 4 AST (SGOT) or ALT (SGPT) of any duration
- All other clinically significant NCI common terminology criteria that are CTCAE grade \geq 3 (except for electrolyte disturbances responsive to correction within 24 h, diarrhea, nausea and vomiting that responds to standard medical care)

An AE must be clinically significant to define DLT e.g. nausea and vomiting < grade 3, alopecia, study drug-related fever, electrolyte abnormalities (including K, Na, Cl, HCO3, Mg, Ca, bilirubin) that are grade <3 will not define the DLT.

Monitoring for toxicity will follow a Bayesian-based rule for the probability that the rate of DLT exceeds a maximal tolerated level of 33%. We will assume a Beta (1,2) prior,

which is prior information equivalent to one DLT observed in three treated patients. This minimally informative prior is justified as there is some clinical experience with the investigational therapy. Early termination for toxicity will be considered based on a posterior probability above 75% that the toxicity rate exceeds 33%. Stopping boundaries for toxicity monitoring are provided in the table below.

# Patients (inclusive)	Stop the trial if there are at least this many DLTs total:
1 to 2	Never stop with this many patients
3	2
4 to 6	3
7 to 9	4
10 to 12	5
13 to 15	6
16 to 18	7
19 to 21	8
22 to 24	9
25 to 27	10
28 to 29	11
30	Always stop with this many patient

12.3.2 Evaluation of response:

Only those patients who have measurable disease present at baseline, have received at least two cycles of therapy, and have had their disease re-evaluated will be considered evaluable for response. Each patient will be assigned one of the following categories: 1) complete response, 2) partial response, 3) stable disease, 4) progressive disease, 5) early death from malignant disease, 6) early death from toxicity, 7) early death because of other cause, or 9) unknown (not assessable, insufficient data). [Note: By arbitrary convention, category 9 usually designates the "unknown" status of any type of data in a clinical database.]

Patients in response categories 4-9 should be considered to have a treatment failure (disease progression). An incorrect treatment schedule or drug administration does not result in exclusion from the analysis of the response rate.

13 Data Reporting / Regulatory Requirements

Adverse event lists, guidelines, and instructions for reporting adverse events can be found in Section 10.

